3.6 Summaries to Support the Secondary Objectives

The secondary objectives of this study are:

- 1) To evaluate the safety and tolerability of tralokinumab.
- 2) To evaluate the immunogenicity (IM) of tralokinumab.

3.6.1 Safety and Tolerability of Tralokinumab

3.6.1.1 Adverse Events

An adverse event (AE) is defined in the protocol as any medical occurrence in a patient or clinical investigation subject administered a pharmaceutical product and which does not necessarily have a causal relationship with this treatment. An AE can therefore be any unfavorable and unintended sign (including an abnormal laboratory finding), symptom, or disease temporally associated with the use of a medicinal product, whether or not considered related to the medicinal product. An AE includes but is not limited to any clinically significant worsening of a subject's pre-existing condition. An abnormal laboratory finding (including ECG finding) that requires an action or intervention by the investigator, or a finding judged by the investigator to represent a change beyond the range of normal physiologic fluctuation, was considered an AE.

A serious adverse event (SAE) is any AE that may be one or more of the following: results in death; is immediately life-threatening; requires inpatient hospitalization or prolongation of existing hospitalization; results in persistent or significant disability/incapacity; is a congenital anomaly/birth defect in offspring of the subject; is an important medical event that may require medical intervention to prevent one of the outcomes listed above.

The reporting period for AEs and SAEs is the period immediately following the time that written informed consent is obtained through the end of study (Study Day 57).

Adverse events may be treatment emergent (ie, occurring after initial receipt of investigational product) or non-treatment emergent. A non-treatment-emergent AE is any new sign or symptom, disease, or other untoward medical event that begins after written informed consent has been obtained but before the subject has received investigational product. A treatment emergent event is defined as a new sign, symptom, disease, or other untoward medical condition occurring after receipt of investigational product, or a worsening of a subject's pre-existing condition.

Adverse events will be coded using a Medical Dictionary for Regulatory Activities (MedDRA). The version of MedDRA used will be indicated in the tables/listings.

Per protocol, (sections 6.1.3.1 and 6.3.2), hepatic function abnormality was defined as an adverse event of special interest (AESI): i.e., any increase in ALT or AST greater than 3 x ULN, and concurrent increase in bilirubin to greater than 2 x ULN. [Concurrent findings are those that derive from the same blood draw, or from separate blood draws taken within 8 days of each other.]

Adverse events (AE) and serious adverse events (SAE) will be summarized by MedDRA system organ class, preferred term, severity, and relationship to investigational product. Summary tabulations to be provided for adverse events include the following:

Summary	Population
Number of Subjects with Non-Treatment Emergent Adverse Events	Safety
Rate Summary of Non-Treatment Emergent Adverse Events	Safety
Number of Subjects with Treatment Emergent Adverse Events	Safety
Rate Summary of All Treatment Emergent Adverse Events	Safety
Number of Subjects with Treatment Emergent Adverse Events by Highest Severity	Safety
Number of Subjects with Treatment Emergent Adverse Events Sorted by Frequency	Safety
Number of Subjects with Related Treatment Emergent Adverse Events	Safety
Number of Subjects with Related Treatment Emergent Adverse Events by Highest Severity	Safety

Summary	Population
Number of Subjects with Non-Treatment Emergent Serious Adverse Events	Safety
Number of Subjects with Treatment Emergent Serious Adverse Events	Safety
Number of Subjects with Treatment Emergent Serious Adverse Events by SAE Criteria	Safety
Number of Subjects with Related Treatment Emergent Serious Adverse Events	Safety
Number of Subjects with Treatment Emergent Serious Adverse Events by Highest Severity	Safety
Non-Treatment Emergent Adverse Events Resulting in Death	Safety
Treatment Emergent Adverse Events Resulting in Death	Safety
Number of Subjects with Treatment Emergent Adverse Events Resulting in Permanent Discontinuation of Study Drug	Safety

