4.2.2 Exclusion Criteria

Any of the following would exclude the subject from participation in the study:

- 1) Concurrent enrollment in another clinical study where the subject is receiving an investigational product
- 2) Employees of the clinical study site or any other individuals involved with the conduct of the study, or immediate family members of such individuals
- 3) Pregnant or breastfeeding women
- 4) Individuals who are legally institutionalized
- 5) Receipt of any marketed or investigational biologic agent within 4 months or 5 half lives prior to screening, whichever is longer
- 6) Receipt of any investigational nonbiologic agent within 3 months or 5 half-lives prior to screening, whichever is longer
- 7) Receipt of any excluded concomitant medication as listed in Section 4.6.2 within 14 days (or 5-half lives, whichever is longer) of screening
- 8) History of a deterioration in asthma that required a burst of systemic corticosteroids within 3 months of screening, up to and including Day 1
- 9) History of hospitalization (overnight admission) for asthma during the 6 months prior to screening
- 10) History of intubation for the management of a deterioration in asthma
- 11) History of allergy or reaction to any component of the investigational product formulation or history of anaphylaxis following any biologic therapy
- 12) Current tobacco smoking or cessation of smoking for ≤ 3 months prior to screening
- 13) Any active medical condition other than asthma, that in the opinion of the investigator and/or medical monitor may compromise the safety of the subject in the study or interfere with evaluation of the investigational product or reduce the subject's ability

- to participate in the study (subjects with atopic skin conditions and allergic rhinitis are permitted)
- 14) History of any known primary immunodeficiency disorder excluding asymptomatic selective immunoglobulin A
 - 15) Clinical characteristics (eg, daytime symptoms, nocturnal symptoms, limitations of activities, need for reliever treatment and lung function PEF/FEV₁) at either screening or Day 1 that are consistent with uncontrolled asthma as described in GINA guideline ([GINA, 2010; Appendix 2](#))
 - 16) History of a clinically significant infection (eg, requiring antibiotics or antiviral medications) from 30 days prior to screening, up to and including Day 1

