6.2.2.2 Relationship to Protocol Procedures

The investigator is also required to provide an assessment of relationship of SAEs to protocol procedures on the SAE Report Form. This includes nontreatment-emergent SAEs (ie, SAEs that occur prior to the administration of investigational product) as well as treatment-emergent SAEs. A protocol-related SAE may occur as a result of a procedure or intervention required during the study (eg, blood collection, washout of an existing medication). The following guidelines should be used by investigators to assess the relationship of SAEs to the protocol:

Protocol related: The event occurred due to a procedure/intervention that was described in the protocol for which there is no alternative etiology present in the subject's medical record.

Not protocol related: The event is related to an etiology other than the procedure/intervention that was described in the protocol (the alternative etiology must be documented in the study subject's medical record).

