7.2 Analysis Populations

The PK population includes all subjects who receive the investigational product and who have at least one detectable post dosing tralokinumab serum concentration

The safety population includes all subjects who receive any investigational product

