3.2 Subject Populations

Two populations have been defined in this study, the PK population and the Safety Population.

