3.2.2 Safety Population

The safety population includes all subjects who receive the investigational product.

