3.3 Baseline Characteristics

Several summaries, which include Subject Population for Evaluation, Number of Subject Enrolled by Site, and Status of Enrolled Subjects, will be provided to describe the study population. These summaries will aid in interpretation of the assessment of the primary, secondary and exploratory objectives and provide an overview of study conduct.

The summary of the number of subjects enrolled by site will be sorted by site number and will contain the primary investigator's name/location.

The summary of enrolled subject status at end of study will include an enumeration of the number of subjects who completed the study and the number who did not complete the study due to the following reasons: adverse event, death, lost to follow-up, withdrawal of consent, and other.

All the baseline characteristics (demographics, baseline disease characteristics, medical history and asthma history), concomitant asthma and non-asthma medications taken prior to study entry, and concomitant asthma and non-asthma medications taken during the study, will be summarized for the PK population since the primary objective of this study is PK assessment.

Demographics and baseline disease characteristics will be summarized for the overall population and by age cohort

The following demographic characteristics will be summarized: age in years, gender, race, ethnicity, weight, height, and Body Mass Index (BMI). BMI is calculated as follows:

$BMI = weight (kg) / [height (m)]^2$

The summary of baseline disease characteristics will include descriptive statistics for whole blood eosinophil count, and spirometry [pre- and post-bronchodilator FEV_1 , pre-bronchodilator FEV_1 % predicted, % reversibility in FEV_1 , FVC, FVC % predicted, and FEV1/FVC ratio].

Prior and concomitant medications will be coded using the latest available version of AstraZeneca Drug Dictionary (AZ DD). All prior and concomitant medications will be summarized.

Summary	Population
Study Populations for Evaluation	NA
Number of Subjects Enrolled by Site	Safety
Status of Enrolled Subjects at End of Study	Safety
Demographics	PK (overall population and by age cohort)
Baseline Disease Characteristics	PK (overall population and by age cohort)
Summary of Medical History	РК
Summary of Asthma History	РК
Summary of Asthma Medications at Study Entry	РК
Summary of Asthma Medications After Enrollment	РК
Summary of Non-Asthma Concomitant Medications at Study Entry	РК

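### Pre-dose adverse event tables and the subject status table are restricted to dosed subjects, so pre-dose deaths and events that prevent dosing cannot be counted in them

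*SAP*

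**What the plan says.** **Populations.** SAP section 3.2 states: "Two populations have been defined in this study, the PK population and the Safety Population". Section 3.2.2 reads: "The safety population includes all subjects who receive the investigational product". Protocol section 7.2 agrees: "The safety population includes all subjects who receive any investigational product". The PK population also requires a dose, plus a detectable post-dose concentration. Neither document defines a consented, screened or entered population.

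**Events.** SAP section 3.6.1.1 defines a non-treatment-emergent AE as one that starts after consent and before the product is received. It sets the reporting period for AEs and SAEs from consent to Day 57. Its table list includes four summaries of such events: subjects with AEs, AE rate, "Number of Subjects with Non-Treatment Emergent Serious Adverse Events" and "Non-Treatment Emergent Adverse Events Resulting in Death". The population entered against each is Safety.

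**Collection.** Protocol sections 6.4.1 and 6.4.2.1 start AE and SAE reporting at consent. Section 6.2.2.2 has the investigator judge SAEs against protocol procedures: "This includes nontreatment-emergent SAEs (ie, SAEs that occur prior to the administration of investigational product) as well as treatment-emergent SAEs".

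**Disposition.** In SAP section 3.3, the table "Status of Enrolled Subjects at End of Study" is also on Safety, as is the enrolment-by-site table. The reasons for non-completion listed there include adverse event and death.

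**The concern.** Whether a subject belongs to the Safety population depends in part on the outcome being tabulated. Some pre-dose events stop the subject from being dosed, and that removes the event from the tables that carry its name. Exclusion 8 in protocol section 4.2.2 is a clear case: "History of a deterioration in asthma that required a burst of systemic corticosteroids within 3 months of screening, up to and including Day 1". Exclusion 16 works the same way for a clinically significant infection up to and including Day 1.

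What is at stake is the tabulated account of screening in minors. Screening is not free of procedures: section 5.2.3 has medicines withheld for 6 to 24 hours before spirometry, and section 5.2.3.1 gives up to 400 µg of salbutamol and foresees side effects. The protocol asks for pre-dose SAEs to be judged against procedures, but the tables leave out those in subjects who were never dosed.

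The status table has a related gap. Protocol section 4.3 and SAP section 2.2.1 treat a subject as entered once the IXRS assigns a kit number, which comes before dosing. Protocol section 4.2.4 foresees subjects who do not receive tralokinumab and allows them to be replaced. Such a subject is entered but does not appear in the table of enrolled subjects' status.

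**Working it through.** The plan gives no figure to reproduce. The check is set logic, plus one sum for the length of the period concerned.

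**Inputs**
- Safety = subjects who received the product (SAP 3.2.2; protocol 7.2).
- Non-treatment-emergent event = onset after consent and before the dose (SAP 3.6.1.1; protocol 6.1.1).
- Population label of the four tables = Safety (SAP 3.6.1.1).
- Population label of the status table = Safety (SAP 3.3).

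**Rule that follows.** Each of the four tables counts events that began before the dose, in subjects who were later dosed.

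**Records put through the rule**

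| Record | Collected? | In Safety? | Counted in the pre-dose tables? |
|---|---|---|---|
| Consented; asthma admission with a systemic steroid burst on Day -5; not dosed | Yes, as an SAE | No | 0 |
| Consented; dies during screening | Yes, as an SAE | No | 0 |
| Consented; cold on Day -10; dosed on Day 1 | Yes, as an AE | Yes | 1 |
| AE begins before the dose; dosed; dies of that AE afterwards | Yes, as an SAE | Yes | 1, including in the death table |

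The last row shows that the death table is not empty by construction. What it cannot hold is a death that occurs before dosing.

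**Status table.** Entered through the IXRS and not dosed means not in Safety, so the count is 0. The same holds for the enrolment-by-site table.

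**Length of the period.** Protocol section 3.2 gives up to 30 days for consent, 14 for screening and 57 for follow-up: 30 + 14 + 57 = 101, which agrees with the stated total. The pre-dose part is at most 30 + 14 = 44 days, and 44/101 = 0.436, or about 44%. If screening starts at the consent visit, the 30-day part falls away.

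**Tables affected.** Four pre-dose event tables plus two enrolment tables (by site, and status) makes six labels.

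**The case against.** The strongest reply is that nothing in the study's objectives depends on these tables. The safety endpoint in protocol section 7.3.2 is the incidence of treatment-emergent AEs, and those tables are rightly on dosed subjects. The pre-dose tables can be read as the pre-dose history of the dosed cohort, and neither document says they were meant to cover screen failures. Every SAE from consent goes to the sponsor within 24 hours of being identified (protocol 6.4.2.2), and the procedure-relationship judgement is made on the SAE form, not in a table. Listings under SAP section 3.1 are not expressly confined to dosed subjects. A separate programming plan, not available here, holds the table specifications. Protocol section 5.1.1 allows one repeat screening visit for time-sensitive exclusions, and a subject dosed after it is in Safety. For disposition, SAP section 3.3 also plans *Study Populations for Evaluation*, with population NA, where the number entered but not dosed may appear.

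Most of this stands as a limit on the consequences. It does not remove the gap. The SAP does not say that events in undosed subjects will be listed, does not title the four tables as covering dosed subjects only, and labels them Safety without qualification. A count of undosed subjects in the populations table would not give their status or reason for stopping.

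Three stronger readings are tempting, and the documents support none of them:

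- **That the pre-dose AE rate is biased low beside the treatment-emergent rate.** Neither document plans that comparison. If one were made, using the same dosed subjects in both periods is defensible, whereas adding screen failures to one side only would compare different people.
- **That only mild events survive into the tables.** Dosing turns on the eligibility criteria, not on AE grade. Some screening failures also reflect a state present before consent and are not AEs at all.
- **That a percentage can be put on the undercount.** This needs the pre-dose event rate and the share of events that prevent dosing. The documents give neither.

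**Conclusion.** The point holds for the SAP's tables. Followed as written, the plan gives a count of zero to any death before dosing and to any pre-dose AE or SAE that prevents dosing, in all four tables of non-treatment-emergent events. It also omits any entered but undosed subject from the enrolment-by-site and status tables. This follows from the definitions and rests on no assumed rate.

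The practical size is unknown and may be nil in a study of 20 subjects: the documents do not say how many consented subjects will fail screening because of an event. The effect is confined to the tabulated record of screening and procedure-related events. Conclusions about tralokinumab do not change, and SAEs are not lost to the sponsor. The conclusion assumes that the population labels in the SAP are applied literally and that the programming plan does not override them.

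**What to change.** 1. Add a third population to SAP section 3.2, all consented subjects, defined by signed consent and assent. Do not define it by the subject identification number. Protocol section 4.1 assigns that number once consent is obtained, but Table 5.1-1 and section 5.1.1.2 assign it at Visit 2, up to 30 days after the consent visit. An event in between could then fall outside the population again.
2. Put the four non-treatment-emergent tables on that population, with separate columns for subjects later dosed and never dosed, each with its own denominator.
3. Put the enrolment-by-site and status tables on all subjects entered through the IXRS, and add a row for entered, not dosed.
4. Leave every treatment-emergent table on Safety.

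If the sponsor prefers to keep the present tables, the minimum is a title or footnote saying that they cover dosed subjects only, and a sentence committing to list all events in consented subjects who were not dosed.

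The cost is a new population definition, six changed labels, and the cleaning and coding of a few screen-failure AE records. No new event collection is needed, since AEs and SAEs are already reported from consent. Demographics for undosed subjects are optional under protocol section 9.1, but these tables do not need them.

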3.6.1.2 Clinical Laboratory Tests

Clinical laboratory safety tests including serum pregnancy tests will be performed in a central clinical laboratory. Urine pregnancy tests may be performed at the site using a licensed test (dipstick). Abnormal laboratory results should be repeated as soon as possible (preferably within 24-48 hours). These repeat tests may either be performed by the central clinical laboratory or by a laboratory local to the site as clinically indicated.

Laboratory measurements will be evaluated with descriptive statistics (N, mean, median, standard deviation, minimum and maximum) for lab results and changes from baseline at each collection time point. Unless otherwise indicated, baseline will be defined as the last valid measurement prior to dosing. The geometric mean may be used to summarize the data if it is thought that the numbers are too small for the usual summary statistics to provide value meaning to interpretation of the data.

All laboratory values will be included in the listings and values outside of the normal range will be flagged. For laboratory values reported as lower than the limit of quantification (LLOQ), a value equal to half of the limit of quantification will be imputed in the summaries.

However, all laboratory measurements will be included in the data listings as reported without any imputation.

Summary	Population
Hematology Results	Safety
Serum Chemistry Results	Safety
Change from Baseline in Hematology Results	Safety
Change from Baseline in Serum Chemistry Results	Safety
Shift Table for Hematology Results	Safety
Shift Table for Serum Chemistry Results	Safety
Summary of Urinalysis Results	Safety

3.6.1.3 Vital Signs

Vital signs (blood pressure, temperature, pulse rate, and respiration rate) will be obtained at all visits. On Day 1 vital signs will be obtained before investigational product administration. The values thus obtained will be defined as the baseline values. Changes from baseline in the quantitative measurements will be derived from these.

After investigational product administration, subjects will be monitored for immediate drug reactions; vital signs will be taken at 15, 30, 45 minutes, and 1, 4, and 8 hours after dosing. Discharge from site will be determined by the investigator.

Vital signs (blood pressure, temperature, pulse rate, and respiration rate) will be obtained at visits 3, 4, 7, 9, and 12 after the subject has been resting for at least 5 minutes.

Vital sign (blood pressure, temperature, pulse rate, and respiration rate) results and change from baseline for vital sign results will be summarized using descriptive statistics. In addition, a listing of vital signs data will be generated.

Summary	Population
Summary of Vital Sign Results	Safety
Change from Baseline for Vital Sign Results	Safety

3.6.1.4 ECG

Computerized 12-lead ECG recordings will be obtained after the subject has been supine for at least 10 minutes. Each lead will be recorded for at least 3-5 beats at a speed of 25 mm/sec paper speed and 10 mm/mV amplitude. Heart rate, PR, QRS, QT and QTc intervals (msec) will be recorded from the 12-lead ECG. The principal investigator or a designated sub-investigator will be responsible for the overall interpretation and determination of clinical significance of any potential ECG findings..

For ECGs, baseline is defined as the value obtained from the screening visit. The number of subjects with qualitative ECG results or findings will be produced. In addition, the observed values for quantitative assessments (heart rate, PR, QRS, QT, and QTc intervals) and the change from screening in quantitative assessments will be summarized with descriptive statistics. All ECG data will be listed.

Summary	Population
Summary of Qualitative ECG Findings/Results	Safety
Summary of Quantitative ECG Test Results	Safety
Change from Screening in Quantitative ECG Test Results	Safety

